6.2.2.2 During Diet Transition Period

During the diet transition period, CGM data will be reviewed by the treating physician and used to guide medication titration.

If the risk of hypoglycemia has not been adequately reduced, doses of sulfonylureas, meglitinides, or possibly other glucose-lowering medication(s) should be further reduced or discontinued if appropriate and in the clinical judgment of the participant's treating physician.

In the event of severe hypoglycemia, study staff will document these episodes on the Adverse Event form.

6.2.3 Rescue Criteria

Participant with a fasting glucose > 270 mg/dL, confirmed by repeat measure, and/or associated with symptoms of abdominal pain, nausea, vomiting or dehydration will trigger the recommendation to be

evaluated by the treating physician and the consideration of intensification of background glucose-lowering medication and/or initiation of new medication.

The above criteria are provided as a guideline. Investigators should always exercise his/her clinical judgement to protect participant's safety.

Medication changes and reasons for the changes will be documented on the eCRFs. Medications used to manage hyperglycemia are non-investigational and will not be provided by the sponsor.

6.3 Proton Pump Inhibitor

Participants will be placed on PPI (Omeprazole 40 mg daily or equivalent) at least one week prior to the index procedure.

6.4 NSAIDs (Non-Steroidal Anti-inflammatory Drugs)

Participants must be off NSAIDs for four weeks after the index procedure. Low dose aspirin (100 mg/day) may be used if needed in combination with prophylactic PPI. If unable to discontinue NSAID for four weeks, the participant should be excluded from the study.

6.5 Anticoagulant and Antiplatelet Medications

If a participant is taking anticoagulant medications, the anticoagulant must be stopped until the International normalized ratio (INR) returns to normal or bridged with low molecular weight heparin (LMWH) prior to the index procedure. The antiplatelet medications must be stopped for 5 days prior to the index procedure. Post procedure, the anticoagulant or antiplatelet medications may be resumed after 48 hours if there is no evidence of bleeding.

The investigator must evaluate the risks of discontinuing these medications based on the overall clinical judgement. If these medications can't be discontinued safely, the participant should be excluded from the study.

6.6 Prohibited Concomitant Medications

6.6.1 Weight-Loss Medications

Study participants will not be allowed to take any weight-loss products during the course of the study, including prescription or over-the-counter (OTC) weight loss medications and herbal products.

6.7 Other Concomitant Medications

Concomitant medications deemed medically necessary for the participant will be allowed during the course of the study; however, any changes in medications will be documented on the Concomitant Medication Log. Medications used during the DMR procedure, such as anesthesia, will not be tracked via the Concomitant Medication Log.

6.8 Participant Education and Lifestyle Counseling

6.8.1 Hypoglycemia

At the onset of the study, participants should be educated on the potential for development of hypoglycemia, the symptoms and signs of hypoglycemia, instruction in the use of continuous blood glucose monitoring to detect hypoglycemia, and instruction on treating hypoglycemia. Symptoms suggestive of hypoglycemia include lightheadedness, tremor, shaking, sweating, tingling, blurred vision, difficulty concentrating, and confusion. With marked hypoglycemia, patients may develop altered consciousness, coma, or seizures.

Participants will use CGM for at least 5 days at baseline and for 28 days after the procedure, followed by a 7-day monitoring at each of the 3-, 6-, 9-, and 12-month follow up visits. Participants should be instructed to promptly contact site staff for any documented or suspected hypoglycemia during the study.

The definition of hypoglycemic episodes can be found in **Appendix A**. Study participants or study staff may identify these episodes.

6.8.2 Transitional Diet

Participants will be educated on the post-procedure transitional diet comprised of 24 hours of clear liquids (water, clear broth, sugar-free popsicles, tea) followed by full liquid diet (dairy-free milk, protein shakes, strained soups) for 3 days, pureed food diet (pureed soup, sugar-free pudding, fat-free yogurt) for 3 days, and soft food diet (such as stew, fish, soft lean meat) for one week, and then transition to a normal diet as tolerated. Participants should be educated on the importance of hydration, especially during the transitional diet period to prevent hypovolemia. Participants should be instructed to contact the study team if s/he is unable to take food and unable to take at least 2 liters of water per day. Participants should also be instructed to avoid dairy products if experiencing diarrhea during the transitional diet period.

6.8.3 Lifestyle Modification Counseling

The lifestyle modification counseling will follow standard of care as outlined in the Standard of Medical Care in Diabetes 2020². The goal is to promote use and adherence to healthy eating patterns, increase physical activity (primarily through daily walking), and to recommend behavioral modification strategies.

6.8.3.1 Nutritional Recommendations

Participants will be educated on healthful eating patterns to improve overall health, emphasizing a variety of nutrient-dense foods in appropriate portion sizes. The nutritional recommendations will be individualized to achieve a healthy body weight goals; to attain individualized glycemic control, and blood pressure, and lipid goals; and to delay or prevent the complications of diabetes. Participants will be educated on controlling portion sizes and intake of carbohydrates/starchy foods; increasing intake of low glycaemic index and high-protein foods, as well as vegetables; and reducing intake of foods high in fat and sugar, and alcohol. The calorie recommendation will follow the recommendations of the Diabetes Prevention Program¹⁰. Participants who weigh ≤ 114 kg (≤ 250 lb) will be prescribed 1200-1500 kcal/d and those > 114 kg (> 250 lb) 1500-1800 kcal/d.

6.8.3.2 Physical Activity Recommendations

Participants will be encouraged to include more physical activity in their daily routine for example: walk more every day, climb the stairs instead of taking the lift or escalators, walk to the next bus stop, walk to shops, ride an exercise bike while watching TV. They will also be encouraged to do more activity in their leisure time such as: going for a walk, bicycling or swimming. They will be asked to start with short periods of low-intensity exercise and increase the intensity and duration slowly. Their goal will be to include 150 minutes a week of moderate intensity and 75 minutes a week of vigorous intensity aerobic activity and muscle strengthening activities more than 2 days a week. Tools such as pedometers or mobile apps maybe recommended (but are not provided) to help individuals increasing their exercise. Any exercise will be adjusted to individual needs and activity levels.

Because of the variation in glycemic response to exercise bouts, participants who are on medications with hypoglycemic risks should be educated to check blood glucose before and after periods of exercise and about the potential prolonged effects (depending on intensity and duration).

6.8.3.3 Behavior Modification

At the same time as the nutritional recommendations and activity advice, participants will be instructed in behavioral modification strategies to promote adherence. Examples of these strategies include estimating

portion size by using diabetes plates, reducing consumption of high sugar, high calorie beverages, putting the fork down between bites, etc.

CGM data will be reviewed with the participant to educate the participant as to what food choices minimize postprandial plasma glucose (PPG) and what physical activity choices directly lower PPG; troubleshoot for those with glucose out of their desired range; and reinforce choices that resulted in desirable glucose consequences.

7 STUDY EVALUATION AND STUDY VISITS

This protocol is developed at the time of the COVID-19 pandemic. To mitigate the risks of potential patient exposure, study assessments and visits may be performed remotely using the site's telehealth platform, and onsite visits maybe limited to the ones necessary for study intervention and the integrity of the study. Participants will be provided with a scale to enable remote weight data collection. If necessary, nurse in-home visits will be used for in-home blood sample collections and vital signs data collection.

7.1 Demographics

Baseline demographic data will be collected to assess participant characteristics that include age, gender, race and ethnicity.

7.2 Medical History and Concomitant Medication

Participant's medical history and baseline medications will be reviewed and documented at screening visit. Changes in medical condition and medication usage will be reviewed, assessed, and documented at each study visit.

7.3 Measurement of Height, Weight, Waist Circumference and Calculation of Body Mass Index (BMI)

For onsite visits:

Height is measured without shoes in cm and recorded to nearest $\frac{1}{2}$ cm.

Body weight should be measured in kilograms (kg), to one decimal, without shoes and only wearing undergarments and an exam gown.

The BMI is calculated in the eCRF using the following

$$\text{BMI} = \text{body weight (kg)} / (\text{height (m)} \times \text{height (m)}) \quad [\text{kg/m}^2 = \text{lb/in}^2 \times 703].$$

Waist circumference is measured with the participant in a standing position with arms down their side and feet together. The measurement is taken at the midway between the lower rib margin and the iliac crest using a non-stretchable measuring tape. The tape should touch the skin but not compress soft tissue. The participant should be asked to breathe normally and the measurement should be taken when the participant is breathing out gently.

The measurement will be recorded to the nearest $\frac{1}{2}$ cm using the same measuring tape throughout the trial.

For remote visits:

Participants will be provided with a scale to enable weight assessment at home. Participants will be instructed to wear only undergarments and no shoes when measuring weight.

Waist circumference will be measured by the nurse who also performs in-home blood sample collection.

7.4 Blood pressure and pulse rate

Systolic and diastolic blood pressure and pulse rate (beats per minute) should be measured in a sitting position after the participant has been resting for at least 5 minutes and by using standard clinical practice at the trial site. For remote visits, the measurements will be performed by a nurse who also performs in-home blood sample collection.

7.5 Physical examination

A physical examination will be performed during onsite visit and will include the following:

- General appearance
- Skin
- Thyroid gland
- Respiratory system
- Cardiovascular system
- Gastrointestinal system including mouth
- Central and peripheral nervous system
- Lymph node palpation

7.6 Electrocardiogram

A 12-lead ECG will be performed and interpreted locally by the investigator or delegate.

An ECG performed for any reason unrelated to the study within 7 days prior to the screening visit is acceptable provided no clinical symptoms suggestive of cardiac disease have occurred in the meantime. If the ECG was performed as a part of routine clinical practice on/before the date when the participant has signed the informed consent, it must be documented in the medical records that the reason for performing the procedure is not related to this study.

7.7 Laboratory Assessments

Local laboratories with appropriate accreditation will be used for all laboratory tests. Specific tests required at each visit are outlined in SoA (**Appendix 2**).

Fasting blood samples will be obtained at the screening and baseline visits, and at Week 1, 4, 12, 24, 36, and 48.

At these fasting visits, participants will not take any food or liquid within the last 8 hours prior to blood sampling, however water is allowed up until 2 hours prior to blood sampling. Participants can take their regular morning medications but should be advised not to take any of their diabetes medications on the morning of their study visit. Participants should bring their diabetes medications to their study visits and take them after blood sampling.

7.8 Mixed Meal Tolerance Test

Following a minimum of 8-hour fast, the participant will undergo an MMTT which involves the consumption of a standardized mixed meal, consisting of 200ml of Ensure Plus and an Optifast bar with a combined calorie of 533 Cal (carbohydrate 63.4g, protein 31.8g, fat 17.4g, Fiber 6.7g) , and collection of timed serial blood samples for measurement of plasma glucose, insulin and C-peptide through 180 minutes after consumption of the standardized meal (with no additional food intake during this time).

The MMTT should be started between 7AM and 11AM. A cannula is placed in a forearm vein. The standardized meal will be consumed within 5 minutes, and the blood samples will be collected within 15 minutes before consuming the standardized meal (ie, “0 minutes”), and at 10, 20, 30, 60, 90, 120, and 180

minutes after consumption. Blood sampling should occur as close as possible to the specified times (± 5 minutes) for the MMTT.

The MMTT will be performed at the time points specified in the SoA (Appendix 2). The test requires the participant to visit to the testing laboratory. If the risk of potential COVID-19 exposure outweighs the benefit of performing the test in the opinion of the Investigator, the investigator may decide not to perform this test but perform tests for HbA1c, FPG and insulin instead. Follow-up MMTT will only be scheduled in participants who had baseline MMTT data.

7.9 Test for *Helicobacter Pylori*

A negative urea breath test or stool antigen test for *H. pylori* is required for study inclusion. The participant should be off antibiotics, antacids, and bismuth for 2 weeks, and not be bleeding before the testing. If the test reveals the participant is positive for *H. pylori*, the participant will be treated accordingly and retested using a stool antigen test. If a breath (performed at least 2 weeks after stopping PPI) or stool retest is negative following completion of the treatment, the participant may be entered into the study. If, after treatment, the participant tests positive for *H. pylori* at the retest, s/he is to be excluded from the study.

7.10 Continuous Blood Glucose Monitoring

Participants will receive a CGM device and be educated on its use after the screening visit and prior to the index procedure. The CGM device will be placed according to the manufacturer's standard instructions. Site staff will assist each participant to set up the mobile App on the participant's personnel mobile phone and enable the sharing features so that the treating physician and other trained study staff can access and monitor the CGM data. The CGM device will be used at the following timepoints.

- Baseline
- Day 1-Week 4
- Week 12, 24, 36, 48

The CGM data will be reviewed by the treating physician for monitoring hypoglycemic events and guiding necessary therapeutic changes.

Additionally, the CGM data will be reviewed by the dietitian and participant during the lifestyle modification counseling sessions.

7.11 Endoscopic Follow-up

The target window for endoscopic follow-up is between 2-5 weeks post procedure. It will be performed when the benefits of performing the test outweigh the risk of potential COVID-19 exposure in the opinion of the Investigator. The procedure and peri-procedural patient care will follow site's routine practice for diagnostic upper GI endoscopy.

7.12 Visit Schedule

A summary of all visits and procedures can be found in SoA (Appendix 2). A more detailed description of each visit and accompanying procedures is described below.

7.12.1 Screening Visit – Visit 1 (within 84 days from the Index Procedure)

To limit in-person visit, the screening visit may be performed remotely. Screening BMI eligibility will be based on self-reported height and weight. A screening consent may be used optionally to facilitate site-specific workflow. Potentially eligible participants will be scheduled for laboratory tests at the study laboratory. The following procedures/assessments will be performed during this visit:

- Informed consent prior to the conduct of any study-related procedures

- Inclusion and exclusion criteria
- Demographics
- Medical history including diseases, disorders and medications
- Diabetes history including diabetes medications
- Laboratory tests:
 - Hematology (CBC with differentials)
 - Metabolic panel (liver and renal function)
 - Fasting serum C-peptide
 - Anti-GAD
 - HbA1C
- H. Pylori (breath or stool test)
- Pregnancy test for females capable of becoming pregnant
- Registration on screening log

Once all data including testing results related to the screening have been obtained, the investigator will review the participant's eligibility for the study. If deemed eligible, participant will be scheduled for the baseline visit.

Eligible participant must meet all the inclusion criteria and none of the exclusion criteria with one exception. If a participant has met all other criteria except that s/he has been on stable glucose-lowering medication(s) for less than 12 weeks at the time of screening visit, the participant can be scheduled for baseline visit such that s/he will be on stable medication for 12 weeks at the time of baseline visit.

It is recognized that COVID-19 restrictions may cause delays in scheduling the index procedure, resulting in the screening visit being out of window. In case the screening visit is out of the visit window, the investigator will reassess the participant's eligibility by evaluating any changes in the participant's medical history and medications. The investigator may decide to repeat certain screening tests based on his/her medical judgement. If the investigator determines that the participant remains eligible for participating in the study, the participant may proceed to Baseline visit. Investigator's assessment and any repeated test results will be documented on eCRFs.

7.12.2 Baseline Visit – Visit 2 (within 28 days prior to the Index Procedure)

This visit will be performed onsite. The following evaluations/procedures are to be performed. Participant's study eligibility will be reconfirmed at this visit.

- Informed Consent if a screening consent was used previously
- Physical examination
- Body measurements including weight and waist circumference
- Vital signs
- Adverse event (changes in medical history)
- Concomitant medications
- Diabetes medications review
- 12-lead EKG
- Laboratory tests:
 - Hematology (CBC with differentials)
 - Metabolic panel
 - Glycemic parameters (HbA1C, MMTT, HOMA-IR)
 - Fasting lipid panel
 - Lipase, Amylase
 - Serum iron, transferrin, saturation, ferritin, serum folate, Vitamin D, Vitamin B12
- H. Pylori breath or stool test
- Pregnancy test for females capable of becoming pregnant

- Assessment for eligibility
- Preparation with gastroenterologist for procedure, medication management per Section 6.
- Diabetes education, including handout and instruction on CGM use
- Treating physician review of diabetes history and titration of glucose-lowering medications per Section 6.2
- Review CGM data
- Lifestyle counselling

If the participant is no longer eligible for the study due to a change in the participant's condition, such as pregnancy, abnormal blood test values, HbA1C outside of the protocol range, or weight change resulting in a BMI outside of the protocol range, the participant will be excluded from the study and documented as a screen failure.

The screening and baseline visit may be combined if the screening visit falls within the baseline visit window. In this case, data collected during the combined visit will serve as both screen and baseline data.

It is recognized that new COVID-19 restrictions may cause delays in scheduling the index procedure, resulting in the baseline visit out of window. In case the baseline visit is out of visit window, investigator will reassess participant's eligibility by evaluating any changes in participant's medical history and medications, Investigator's assessment will be documented on eCRF. The following tests will be repeated for safety considerations or to serve as baseline data:

- Laboratory tests:
 - Hematology (CBC with differentials)
 - Glycemic parameters (FPG, HbA1C, insulin, HOMA-IR)
- Pregnancy test for females capable of becoming pregnant
- Body measurements including weight and waist circumference (may be collected on Day 0)
- Vital signs (may be collected on Day 0)

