3 STUDY OBJECTIVES AND ENDPOINTS

The objective of this first-in-human study is to assess the feasibility and preliminary safety of the Endogenex device for endoscopic duodenal mucosal regeneration in individuals with type 2 diabetes inadequately controlled on glucose-lowering medications.

The study will also assess, as exploratory endpoints, treatment efficacy, evaluated by changes in glycemic control and liver enzymes post procedure from baseline.

Objectives	Endpoints
Primary 
 • To assess the safety of the Endogenex device for DMR procedure 	
 • Proportion of participants experiencing one or more device- or procedure-related serious adverse events at 12 weeks post procedure.
Secondary 
 • To assess the technical feasibility of the Endogenex device for DMR procedure • To assess changes in glycemic control • To assess changes in liver enzymes 	
 • Procedure success: defined as successful treatment of at least 6 cm of duodenum segment. • Procedure time: defined as the time between the Endogenex catheter insertion and the catheter removal. • Change from baseline in glycemic parameters post index procedure, by visits 
 ○ HbA1c ○ Fasting plasma glucose (FPG) ○ Insulin-resistance by HOMA-IR ○ Post prandial plasma glucose (PPG), Beta cell function, disposition index by mixed meal tolerance test (MMTT) • Proportion of treated participants with an HbA1c improvement of 0.3% or more at 24 weeks from baseline • Proportion of treated participants with an HbA1c improvement of 0.3% or more at 24 weeks from baseline and maintained at 48 weeks • Change in weight from baseline by visit • Change in glucose-lowering medication usage • Change in liver enzyme from baseline at 24 weeks 
 ○ Alanine Aminotransferase (ALT) ○ Aspartate Aminotransferase (AST) • Change from baseline in blood pressure and lipid profile by visit

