7.12.3 Index Procedure Visit – Visit 3 (Day 0)

See **Section 6.1** for details of the index procedure and post procedure instructions.

The following assessments/procedures will be performed.

- Handout participant study ID card
- Vital signs prior to discharge
- Concomitant medications
- Assessment of AEs
- Diabetes review and medication titration by treating physician
- Initiate CGM prior to discharge

Participants will be instructed on transitional diet, the importance of hydration, use of CGM for 4 weeks post procedure, and be educated on monitoring hypoglycemic events.

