9.1.4 Abnormal Pancreatic Enzyme Levels

Changes in serum amylase, lipase levels post procedure should trigger assessment for potential pancreatic injury.

The diagnosis of acute pancreatitis requires two of the following three features³:

- Abdominal pain consistent with acute pancreatitis (acute onset of a persistent, severe, epigastric pain often radiating to the back)
- Serum lipase and/or amylase level at least three times greater than the upper normal limit
- characteristic findings of acute pancreatitis on imaging.

For all confirmed events of pancreatitis, the following additional information should be reported if available:

- Signs and symptoms of pancreatitis
- Specific laboratory test supporting a diagnosis of pancreatitis:
- Imaging performed and consistency with pancreatic disease
- Treatment for and complications of the event
- Relevant risk factors for pancreatic disease
- Family history of pancreatitis

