All mean and median values will be formatted to one more decimal place than the measured value. Standard deviation values will be formatted to two more decimal places than the measured value. Minimum and maximum values will be presented with the same number of decimal places as the measured value.

The number and percentage of responses will be presented in the form XX (XX.X%).

- All summary tables will include the analysis population sample size (i.e., number of patients).
- Relative Study Day 1 is defined as the day the patient underwent the DMR study procedure. All study days are determined relative to the day the patient underwent the DMR study procedure.
- Baseline values will be defined as those values recorded immediately prior to the DMR study procedure.
- Change from baseline for ratio data will be calculated as follows:
$$\text{Change} = \text{Post-Procedure value} / \text{baseline value}.$$
- Change from baseline for differences will be calculated as follows:
$$\text{Change} = \text{Post- Procedure value} - \text{baseline value}.$$
- Missing data may have an impact upon the interpretation of the trial data. However, given the feasibility nature of this study, coupled with the number of patients within a Comparison Set, multiple imputation will not be attempted. The primary presentation of the results will be based on the observed data. A methodology is defined in this section for addressing missing dates.
- Date variables will be formatted as DDMMYY for presentation; SAS Date9. format.
- Months will be converted to days by dividing by 30.42 and rounding up to achieve an integer value.
- SAS® Version 9.4 will be the statistical software package used for all data analyses.
- All data from this study will be presented in a listing.
- Table and listing numbering will follow ICH guidelines for post-text table and listing numbering.

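### When COVID-19 delay puts the baseline visit out of window, the required repeat tests omit the metabolic panel, fasting lipids and lipase/amylase, so these baselines can be older than 28 days with no stated limit

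*Protocol*

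**What the plan says.** The heading of Protocol 7.12.2 sets the baseline visit "within 28 days prior to the Index Procedure", and the Schedule of Activities gives the window as -28 to -1 days. The visit includes blood count, metabolic panel, HbA1c, mixed meal tolerance test (MMTT), HOMA-IR, fasting lipids, lipase and amylase, an iron and vitamin panel, body measurements, vital signs and review of CGM data.

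The same section then covers COVID-19 delay. "In case the baseline visit is out of visit window", the investigator reassesses eligibility from changes in medical history and medications and documents the assessment. The protocol adds: "The following tests will be repeated for safety considerations or to serve as baseline data". The tests named are blood count; FPG, HbA1c, insulin and HOMA-IR; a pregnancy test where relevant; weight and waist; and vital signs. The last two groups may be collected on Day 0.

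Several places rely on the tests that are not named. Protocol Section 3 lists "Change in liver enzyme from baseline at 24 weeks" for ALT and AST, and change from baseline in lipid profile by visit. Protocol 9.1.4 says: "Changes in serum amylase, lipase levels post procedure should trigger assessment for potential pancreatic injury". Exclusion 28 is an eGFR limit, with a different limit for the insulin cohort in Appendix 4. SAP Section 7 states: "Baseline values will be defined as those values recorded immediately prior to the DMR study procedure".

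**The concern.** The repeat list has two stated purposes, safety and baseline data, and it leaves out blood tests that serve each. A delayed participant can have an HbA1c baseline taken shortly before the procedure and ALT, AST and lipid baselines taken much earlier. Any change in liver enzymes or lipids during the delay is then counted as change after the procedure. In a single-arm study no control group is available to show that drift.

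Lipase and amylase are scheduled only at baseline and Week 1, so the old value is the only scheduled pre-procedure comparator. Creatinine and eGFR belong to the omitted metabolic panel, so eligibility on renal function may rest on an old measurement.

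The protocol's own experience shows why this matters. Appendix 4, Section 1 reports an iron deficiency that could not be classified as new or pre-existing because the baseline test had been missed. It also reports a Week 1 ALT/AST elevation counted as device- or procedure-related. An out-of-date baseline creates a similar difficulty of attribution.

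**Working it through.** There is no stated figure to reproduce. The check is a comparison of lists, followed by window arithmetic.

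**Step 1. Baseline tests against required repeats (Protocol 7.12.2).**

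| Baseline item | Required repeat if out of window? | Used for |
|---|---|---|
| HbA1c, FPG, insulin, HOMA-IR | Yes | Glycemic endpoints |
| Weight, waist, vital signs | Yes | Weight and blood-pressure endpoints |
| Blood count | Yes | Safety |
| Metabolic panel (ALT, AST, creatinine, eGFR) | No | Liver endpoint; eGFR exclusion |
| Fasting lipids | No | Lipid endpoint |
| Lipase, amylase | No | Change-based check in 9.1.4 |
| MMTT | No | Meal-test endpoints |
| CGM | No | Eligibility and safety; an endpoint in the SAP only |

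**Step 2. Is there another measurement, or an age limit?** Day 0 (Protocol 7.12.3) adds no laboratory tests, and CGM is started there before discharge. The baseline definition in SAP Section 7 gives no maximum age. The visit table in SAP 8.6 shows -28 to -1 for Baseline, but that table is introduced as the rule for assigning unscheduled visits. It does not say that an older baseline is to be dropped.

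**Step 3. Intervals.** Let D be the age of the baseline value in days at the procedure. Week 1 is day 7 ± 2, so at latest day 9. Week 24 is day 168 ± 7, so at latest day 175.

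- Lipase/amylase, baseline to Week 1: at most D + 9.
- ALT/AST and lipids, baseline to Week 24: at most D + 175.

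In window, D is at most 28, giving 28 + 9 = 37 and 28 + 175 = 203 days. Out of window, D has no stated limit. The values of D below 28 days' excess are not in the documents; the rows after the first are assumed for illustration.

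| D (days) | To Week 1 (D + 9) | To Week 24 (D + 175) |
|---|---|---|
| 28 (window limit) | 37 | 203 |
| 60 (assumed) | 69 | 235 |
| 90 (assumed) | 99 | 265 |
| 180 (assumed) | 189 | 355 |

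**Step 4. Effect on a mean.** If k of n participants are delayed and their average drift is d, the mean change is shifted by (k/n) × d. Neither k nor d is given. For n, Protocol Section 5 plans 50-60 participants and Appendix 4 plans 20-30 in the insulin cohort, with efficacy analyzed by cohort. One delayed participant therefore carries 1/60 = 1.7% to 1/50 = 2.0% of the non-insulin cohort, or 1/30 = 3.3% to 1/20 = 5.0% of the insulin cohort.

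**The case against.** The strongest defense is that this is a COVID-19 contingency affecting an unknown and perhaps small number of participants. It leaves the primary endpoint and the main glycemic measures intact and touches only secondary endpoints that the protocol summarizes descriptively. That stands, and it limits the weight of the point. Protocol Version O is dated 30 Sep 2023 and enrollment was estimated to end in Q2 2023, so new wording may reach few participants; actual enrollment status is not stated.

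A reader might infer more than the documents support:

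- **That nothing else may be repeated.** The list is a required minimum. Investigators may do more, and eligibility must be reassessed. An old value can be used; it need not be.
- **That the diagnosis of pancreatitis is compromised.** The enzyme criterion in 9.1.4 is absolute, at three times the upper normal limit. Only the looser trigger based on changes depends on the baseline.
- **That a post-procedure blood pressure could become the baseline.** The Day 0 list does name "Vital signs prior to discharge", but SAP Section 7 requires a value from before the procedure, and 7.12.3 does not equate the two readings.
- **That 8 of 18 secondary endpoints are affected, with each patient worth 5% or 10%.** The numbering, the groups of 20 and 10, and the CGM endpoint come from an SAP that names REGENT-1-US, Doc. No. 346. The liver and lipid endpoints stand on Protocol 196 alone.
- **That old MMTT and CGM baselines should be discarded.** Protocol 7.8 lets HbA1c, FPG and insulin replace the MMTT when COVID-19 risk outweighs benefit, so leaving it off the list is consistent with that rule. Section 7.8 also says: "Follow-up MMTT will only be scheduled in participants who had baseline MMTT data". Discarding old values would lose scarce data.

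The COVID-19 rationale does not explain the omission of the three blood panels, because a blood draw is already required.

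**Conclusion.** The point holds as a modest, inexpensive improvement. The required repeats omit the metabolic panel, fasting lipids and lipase/amylase, and neither document clearly limits the age of the old values or provides a new measurement. For delayed participants, ALT, AST and lipid changes can include drift over the delay, the change-based enzyme check can use an old comparator, and eGFR need not be remeasured. The primary endpoint, HbA1c, FPG, HOMA-IR, weight and blood pressure are not affected.

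The size cannot be given as a bias, because the number delayed, the length of delay and the drift are all unstated. What can be stated is the loss of an upper bound: 37 days to Week 1 and 203 days to Week 24 in window, with no stated bound outside it. The conclusion assumes that at least one participant's baseline goes out of window and that the site repeats only what is required.

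**What to change.** In Protocol 7.12.2, add the metabolic panel, fasting lipid panel and lipase/amylase to the tests repeated when the baseline visit is out of window. They can be drawn in the fasting venepuncture already needed for FPG and insulin. Repeated within the 28-day window, they restore the 37- and 203-day limits.

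In the analysis plan, keep MMTT and CGM baselines older than 28 days, flag them, and report change from baseline with and without them. For participants already treated, the same flag can be applied to old ALT, AST and lipid baselines.

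As a clarification only, state that repeat weight and vital signs taken on Day 0 are recorded before sedation.

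The cost is short protocol wording, extra tubes for delayed participants, and one small sensitivity summary.
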